*Hypothesis 4:* Significant factors from hypothesis 3 will identify a latent trait that classifies individuals into two types: those who have high SDA and those who have low SDA.

Aim 3: Identify signatures of neural function that underlie SDA.

*Hypothesis 5:* Those with greater SDA will demonstrate reduced event-related potential component amplitudes differences between negative vs. positive feedback about per-trial progress toward a reward. Those with greater SDA will demonstrate

*Hypothesis 6a:* greater resting state crosstalk between the default mode and fronto-parietal networks and *Hypothesis 6b:* reduced ventral striatal-ventromedial frontal connectivity.

The positive impact of this project will be to advance the translation between preclinical and clinical models and to elucidate distinct mechanisms underlying AUD progression in humans. Importantly, the proposed model uses objective behavior, rather than subjective symptom report. Our human component project is centered on the IARC theme and complements its preclinical components and methodologies. We expect that the results will facilitate the identification and evaluation of pharmacologic and behavioral interventions to minimize the risk of AUD progression risk in drinkers who have yet to manifest treatment resistant behavior.

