### 3.0 Inclusion/Exclusion Criteria

#### Inclusion

- Overtly healthy men and women aged 21 – 55
- Either 25-50 kg or 250-500 kg Lifetime Drinking History (LDH) and recent drinking of at least 7 drinks/week for women and 10 drinks/week men, or any recent drinking or LDH below 500 kg at the discretion of the PI.
- Able to understand/complete questionnaires and procedures in English
- Have venous access sufficient to allow blood sampling

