#### 4.0 Enrollment/Randomization

The project employs a between-participants design. Each participant will undertake 3 or 4 sessions: an interview/screening session, 2 randomly counter-balanced (neutral and aversive stimuli) IV alcohol self-administration sessions, and in a subset of subjects that meet the criteria outlined in the fMRI screen, an fMRI resting state scan. All sessions will take place in the Neural Systems Laboratory at the Indiana Clinical Research Center at Indiana University Hospital or at the Neuroscience Center at Methodist Hospital.

We will consent 300 participants to enroll 150 and complete 100 participants: **a**) 50 individuals who are current drinkers with lower lifetime drinking history, between 25-50 kg ethanol, **b**) 50 individuals who are heavy drinkers with a higher lifetime drinking history of 250-500 kg ethanol, and **c**) individuals below 500 kg ethanol at the discretion of the principle investigator. We will target equal numbers of men and women for inclusion in the lower and higher lifetime drinking groups. Total participant payment will be \$400, plus parking/travel costs.

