#### Aim 2 Hypothesis Testing Plan.

**Hypothesis 3:** Those with greater SDA will have greater AUD severity, greater LDH, greater negative urgency, greater density of familial history of alcoholism, and reduced subjective, behavioral, and electrophysiologic sensitivity to alcohol. To minimize error inflation from multiple univariate tests, we will use structural equation modeling (R3.01 data analysis software using the lavaan statistical package; Figure 6). We will examine AUD severity as an observed independent variable of AUD symptom count. Lifetime Drinking History and density of family history of alcoholism will be observed variables, computed with information collected with Concordia Lifetime Drinking Questionnaire and the SSAGA family history module. Negative urgency will be defined as a latent independent variable, with individual item indicators from the UPPS-P negative urgency subscale. Sensitivity to alcohol will be defined as a latent independent variable with three measured variable predictors: Subjective, behavioral and electrophysiological sensitivity to 60mg/dl alcohol as compared to each individual's baseline response. The dependent measures of interest for sensitivity analysis include Subjective Response to Alcohol, Wisconsin Card Sort, and the Stop Signal Task. The dependent variable will be cumulative work performed for alcohol in the aversive session, defined as an observed variable. We will control for cumulative work performed for alcohol in the neutral session, as well as age, gender, and race, due to their relationship with alcohol use behaviors. Judgment of hypothesis viability will be assessed via **1**) fit indices (recommendations in parentheses: Root Mean Square Error of Approximation ( $RMSEA < 0.10$ ); Tucker Lewis Index ( $TLI > 0.95$ ); and Comparative Fit Index ( $CFI > 0.95$ ) and **2**) pathway loading significance.

**Hypothesis 4:** Significant factors from hypothesis 3 can identify a latent trait that classifies individuals into at two classes of individuals: those who have high and low SDA. The significant phenotypes from hypothesis 3 will be used in a latent class analysis to identify subgroups based on

**Figure 6. Proposed path analysis.** Covariates, error terms, and correlations not shown for simplicity

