their pattern of AUD risk. The Bayesian Information Criteria and entropy will be utilized to determine the number of latent classes that best fit the data. Individuals will be assigned to the latent class with the highest probability, and discrete class membership will be characterized using *post hoc* validators such as number of AUD criteria, negative urgency, family history density and lifetime drinking history. As a final validator, we will test if SDA is different between the classes to determine if class membership reflects motivation to work for alcohol in the face of aversive stimuli.

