### Power Analyses

Alcohol self-administration: Our previous alcohol self-administration work showed effect sizes from 0.49 to 1.31 according to the phenotype of interest. Neurophysiological correlates (EEG/fMRI): Published outcome and feedback-related differences in N200 and P300 amplitudes yield effect sizes from 0.78 to 2.12 for subjects with an AUD versus controls, and 0.62 to 1.6 for the effect of alcohol. There are no standards for power analyses in whole brain connectomics. However, our pilot data showed significant results in  $n=51$ , suggesting  $n=100$  is sufficient to find robust connectivity patterns. We will ensure robustness using permutation tests combined with an extent threshold, or alternatively, using the Permutation Network Framework. Relationship to AUD risk variables: In our pilot data, the relationship between SDA and AUD risk correlates ranged from  $r=0.32 - 0.63$ . With a sample of  $n=100$ , we can detect an effect size of at least 0.32 and still maintain adequate  $power=0.90$ ,  $\alpha=0.01$ . When categorized by groups of  $n=50$  (high/low lifetime drinking history), we can detect differences with an effect size of 0.64 and still maintain adequate  $power=0.90$ ,  $\alpha=0.01$ .

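### Hypothesis 4 compares only numbers of latent classes, so it cannot tell two types of drinker from one graded risk trait

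*Combined protocol and SAP*

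**What the plan says.** Section 2.0 states that the significant Hypothesis 3 factors "will identify a latent trait that classifies individuals into two types", with high and low SDA. Section 7.0 (Aim 2 Hypothesis Testing Plan) repeats this: "Significant factors from hypothesis 3 can identify a latent trait that classifies individuals into at two classes of individuals".

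The analysis has four steps:
- **Indicators.** "The significant phenotypes from hypothesis 3 will be used in a latent class analysis to identify subgroups based on" the pattern of risk. The candidates are at most five constructs: AUD symptom count, lifetime drinking history, negative urgency, family history density and sensitivity to alcohol.
- **Number of classes.** "The Bayesian Information Criteria and entropy will be utilized to determine the number of latent classes that best fit the data".
- **Assignment.** Each person goes to the most probable class.
- **Validation.** Classes are described on AUD criteria, urgency, family density and lifetime drinking. SDA is then compared between classes.

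The plan names no factor or hybrid model, no allowance for correlation within a class, no likelihood-ratio or bootstrap test and no entropy cut-off. The structural equation model for Hypothesis 3 estimates paths to SDA. It does not compare a dimensional structure with a class structure.

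**The concern.** By default, latent class analysis treats indicators as independent within a class. If the only candidates are one, two, three or more classes, any correlation among the indicators can be absorbed only by adding classes. Hypothesis 3 expects the phenotypes to move together with SDA, so correlation among them is likely. The natural rival to two types is one continuous severity dimension. It is never fitted, so it cannot be preferred.

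At stake is the meaning of a Hypothesis 4 result. A two-class solution whose classes differ in SDA would be read as evidence for discrete types, when a graded trait could produce the same output.

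**Working it through.** **Plan's own figure.** There is none for Hypothesis 4. The Power Analyses section covers single correlations and two-group differences, which do not bear on the number of classes.

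**Inputs**
- n = 100 completers: "We will consent 300 participants to enroll 150 and complete 100 participants" (section 4.0).
- Indicators are counts and scores, for example "We will examine AUD severity as an observed independent variable of AUD symptom count". No categorisation is stated, so continuous indicators are the main case.
- Pilot data: "the relationship between SDA and AUD risk correlates ranged from" 0.32 to 0.63 (Power Analyses).
- Correlations among indicators (r) are not given; 0 to 0.5 is assumed. As an anchor, if SDA loads a on the trait, the mean pairwise r is the mean of r_j r_k divided by a². Take five values evenly spaced from 0.32 to 0.63 (sum 2.375, sum of squares 1.188). This gives (2.375² − 1.188)/20 = 0.223 at a = 1 and 0.223/0.64 = 0.35 at a = 0.8.

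**Why correlations cannot decide.** With two classes of shares π and 1 − π whose means differ by d_j, the covariance of indicators j and k is π(1 − π)d_j d_k. With one factor it is λ_j λ_k. Setting λ_j = √(π(1 − π))·d_j makes them identical.

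**BIC arithmetic.** BIC = −2 log L + k ln n, and ln 100 = 4.605. A latent profile model with K classes, J indicators and equal variances has k = KJ + J + K − 1. A second class therefore costs (J + 1) × 4.605, or 23.0 at J = 4. The gain in 2 log L available from equal correlations is roughly −n ln[(1 − r)^(J−1)(1 + (J − 1)r)]. At J = 4:
- r = 0.1: −100 ln(0.729 × 1.3) = 5.4
- r = 0.2: −100 ln(0.512 × 1.6) = 19.9
- r = 0.3: −100 ln(0.343 × 1.9) = 42.8

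So a false second class should be rare at 0.1, borderline at 0.2 and usual at 0.3.

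**Simulation.** One continuous normal trait, no classes, n = 100, BIC over one to three classes, 120–200 samples per cell. The Monte Carlo standard error is about √(0.25/150) = 4 points at most. Entries are the share choosing two or more classes, as ranges over separate runs where there were several.

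| r | 3 indicators | 4 indicators | 5 indicators |
|---|---|---|---|
| 0 | 0–1% | 0–1% | 0–1% |
| 0.1 | 2% | 6% | 4% |
| 0.2 | 27–33% | 49–59% | 71–75% |
| 0.3 | 74–86% | 95–96% | 100% |
| 0.4 | 99–100% | 99–100% | 99–100% |

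**Other indicator scales.** These runs used five constructs with a skewed symptom count and a family density with many zeros. On the raw continuous scale the rate was 100%. Cut at the median it was 38–94%, and in tertiles 10–76%. Sampling lifetime drinking in two separated bands raised the last two to 62–100% and 29–98%. Skewed indicators gave extra classes in 90–99% of samples even when uncorrelated.

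**Adding the Hypothesis 3 gate.** Five normal indicators with r = 0.2–0.5 entered a joint regression on SDA that also contained neutral-session work. Only those with p < 0.05 went forward, and samples with fewer than two survivors counted as no false class. Two or more false classes, as a share of all samples:
- SDA–trait correlation 0.4: 3–7%
- 0.6: 5–33%
- 0.8: 29–86%

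The implied SDA–indicator correlation is the SDA–trait correlation times √r. That is 0.18–0.28 at 0.4, 0.27–0.42 at 0.6 and 0.36–0.57 at 0.8. The pilot range of 0.32–0.63 does not fit the first, overlaps the second and contains the third.

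**Final validator.** A clean median split of a normal trait separates the halves by 2√(2/π) = 1.60 SD. At an SDA–trait correlation of 0.6, SDA would then differ by 0.6 × 1.60 = 0.96 SD. In simulation, SDA differed between false classes in about 50–82% of two-class samples at a correlation of 0.4, in nearly all at 0.6, and in 100% with loadings taken from the pilot range.

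**Entropy.** Scaled entropy divides by ln K, and ln 1 = 0, so it is undefined for one class. It describes separation, not fit.

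**The case against.** A reader might infer that a single continuum will be reported as classes in most samples. The documents do not support that. Only phenotypes significant jointly in Hypothesis 3 go forward, and indicators of one trait compete for the same variance, so few may survive. The documents give no correlations among indicators, and with near-normal indicators the rate is near zero at 0.1 or less. Weakly correlated indicators cut into categories also give lower rates. All of this stands, and the size must be stated conditionally.

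A reader might also infer that Hypothesis 4 cannot be refuted. That goes too far. One class, three classes, or no SDA difference would each count against it. The narrower gap is that no result can favour a dimension over types.

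Entropy is used together with BIC, and a cut-off of 0.80 would leave a passing two-class solution in only 4–12% of equally correlated near-normal samples at r = 0.2–0.3. But the plan states no cut-off, and with the skewed constructs 82–97% of false solutions would pass.

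Finally, Hypothesis 4 is one step within Aim 2. No other hypothesis test uses class membership, and the missing model can be fitted later to the same data. This limits the severity but does not remove the gap.

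**Conclusion.** The point holds in conditional form. As written, Hypothesis 4 cannot separate two types from one graded trait, because the graded trait is not among the models compared.

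If three or more phenotypes enter and correlate at about 0.3 or more, BIC picks two or more classes in about 75–100% of samples of 100 from one continuous trait. At 0.2 it does so in about 30–75%. Allowing for the Hypothesis 3 gate, the overall rate is about 5–33% or 29–86%, for an SDA–trait correlation of 0.6 or 0.8. These figures assume near-normal continuous indicators and a single normal trait; skew raises them.

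The named validators add little. Four of them are candidate indicators themselves, and the SDA comparison usually succeeds for any split of a continuum related to SDA. This is a should-fix on the interpretation of Hypothesis 4. Design, allocation and the other hypotheses are unaffected.

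**What to change.** - **Skew first.** Transform skewed indicators, or model them on a suitable ordinal or count scale.
- **Add the rival.** When at least three indicators are available, fit a one-factor model to the same indicators beside the one-, two- and three-class models, and compare all four by BIC. Three is the minimum: a one-factor model has 3J parameters, against 2J + J(J − 1)/2 means, variances and covariances. That is 9 against 9 at J = 3, but 6 against 5 at J = 2.
- **Decision rule.** Claim two types only if the two-class model beats the one-class, three-class and one-factor models. Otherwise, or with fewer than three indicators, report a continuous risk score and its association with SDA, and make no claim of discrete types.
- **Entropy.** Report it as description only.

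The change needs no new data. With near-normal indicators and a true single trait, the one-factor model was chosen in 77–98% of samples at r = 0.3 and, with four to six indicators, in 58–83% at 0.2. Where two real classes lay at least 2 SD apart on each of four indicators, it won in none of 100 runs.

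The cost is a modest extra analysis and some care over scales. Residual skew can still mimic classes: with one log-normal indicator out of four the one-factor model won only 31%, and with two strongly skewed raw indicators 1–16% at r = 0.2 and 7–45% at r = 0.3.

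### Hypothesis 4 lets the same variables define the latent classes and then validate them, so a class difference on those variables is not evidence of validity

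*Combined protocol and SAP*

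**What the plan says.** The Aim 2 Hypothesis Testing Plan in section 7.0 (Statistical Considerations) links two steps.

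Hypothesis 3 is a structural equation model. Its outcome is SDA (seeking despite aversion), measured as work for alcohol in the aversive session. It has five predictors:
- AUD severity: "We will examine AUD severity as an observed independent variable of AUD symptom count".
- Lifetime drinking and family history: "Lifetime Drinking History and density of family history of alcoholism will be observed variables".
- Negative urgency: "Negative urgency will be defined as a latent independent variable".
- Sensitivity to alcohol, also latent.

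Hypothesis 4 builds classes from whichever of these survive: "The significant phenotypes from hypothesis 3 will be used in a latent class analysis to identify subgroups based on" each person's risk pattern. For the number of classes, "The Bayesian Information Criteria and entropy will be utilized to determine the number of latent classes that best fit the data". For membership, "Individuals will be assigned to the latent class with the highest probability". The classes are then characterized through post hoc "validators such as number of AUD criteria, negative urgency, family history density and lifetime drinking history". The paragraph ends with one more check: "As a final validator, we will test if SDA is different between the classes".

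The plan gives no test, alpha or power for the four named validators. It has no rule that a class indicator may not also be a validator.

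**The concern.** A mixture model forms classes by finding a division of the sample on its indicators. Comparing the classes on those same indicators afterwards largely shows that the algorithm did its work. It describes what the classes look like, but it cannot show that they correspond to anything outside the model. Validation needs a variable that played no part in forming the classes.

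If Hypothesis 3 succeeds as hypothesised, all four named validators will be class indicators. The report could then present AUD risk subgroups as validated on evidence that would also appear if the indicators were merely correlated along a continuum. That matters because Aim 2 is meant to classify people into two types, and two types is a stronger claim than a graded trait.

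**Working it through.** **Step 1: the overlap.** Hypothesis 3 candidates: AUD symptom count, lifetime drinking history, family-history density, negative urgency, sensitivity to alcohol (5). Named validators: AUD criteria count, negative urgency, family-history density, lifetime drinking history (4). All 4 validators are among the 5 candidates. If every predictor is significant, 4 of 4 validators are also indicators; if one of the four fails, 3 of 4 are. There is no overlap only when none of the four is significant, which leaves sensitivity alone or nothing.

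**Step 2: inputs for the size.** The plan states no figure for Hypothesis 4, so there is none to reproduce.
- From the documents: n=100 completers (section 4.0), BIC for class number, assignment to the most probable class.
- Assumed: four normally distributed indicators, all reused as validators; a common correlation of 0 to 0.5 among them; a threshold of p<0.05; a Gaussian latent-profile model with equal within-class variances and local independence. Entropy was not modelled as a selection rule.
- All data were generated with no true classes, 150 to 300 data sets per row.

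**Step 3: the BIC hurdle.** BIC = −2 log L + p ln n. With four indicators, K classes need p = 4K means + 4 variances + (K−1) proportions. So p = 8 for one class and 13 for two. Two classes are preferred when 2 log L rises by more than (13−8) × ln 100 = 5 × 4.605 = 23.0. Under local independence, adding classes is the model's only way to absorb correlation among indicators, so correlation alone can clear this hurdle.

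**Step 4: results.** Where two figures stand in the BIC column, they come from two separate simulations.

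| Assumed correlation | BIC keeps two or more classes | Each reused indicator p<0.05, two classes imposed | At least one of four | All four |
|---|---|---|---|---|
| 0 | 0%, 1% | 55–60% | 99% | 6% |
| 0.1 | 4% | 65–70% | 97% | 24% |
| 0.2 | 47%, 57% | 88–94% | 99% | 69% |
| 0.3 | 95%, 94% | 99% | 100% | 97% |
| 0.5 | 100%, 100% | 100% | 100% | 100% |

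In data sets where BIC itself kept two or more classes, at least one reused indicator differed in 100%. The chance of a spurious validation on at least one variable when BIC decides is therefore about 0.04 × 1.00 = 4% at correlation 0.1, 0.47 × 1.00 = 47% at 0.2 and 0.95 × 1.00 = 95% at 0.3. With skewed indicators BIC kept two or more classes in 100%.

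**Step 5: would a held-out validator cure it?** A variable left out of the class model and uncorrelated with the indicators differed between imposed classes in 3.1–4.9% of tests, close to the nominal 5%. One correlated 0.3 with the indicators still differed in 47–96% across scenarios. Disjoint validators are necessary, but they do not by themselves show that classes exist.

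**The case against.** A reader might infer that the plan would report validated subgroups whether or not any exist. The documents do not support that. The number of classes is not fixed at two: BIC and entropy choose it, and with uncorrelated normal indicators BIC almost always kept one class, leaving nothing to validate. The imposed-class percentages apply only once two classes are accepted. Only predictors significant in Hypothesis 3 are circular, and the validator list is open-ended.

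A reader might also infer that classes must differ on every indicator. They need not. When lifetime drinking was simulated as bimodal, as the 25–50 and 250–500 kg recruitment bands in section 3.0 would tend to make it, and the other indicators were independent of it, lifetime drinking differed in 100% of data sets. The other three differed in only 5–7% with two classes and 12–15% under the BIC solution.

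Third, the wording speaks of characterizing the classes, and the only comparison described as a test is the one on SDA, which is not an indicator. That is fair as far as it goes. But the four variables are called validators and SDA is introduced as the last in that series, so they are given an evidential role. The SDA comparison is not a clean substitute, because the indicators are selected for their association with SDA in the same sample. With SDA unrelated to every predictor, and given at least one predictor selected and two classes imposed, SDA differed in 16–24% of data sets (79 and 85 data sets) against a nominal 5%. That is a separate weakness, and this point does not rest on it.

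**Conclusion.** The overlap is plain in the text and needs no simulation: a Hypothesis 3 predictor that is significant both forms the classes and is listed to validate them. A class difference on such a variable is description, not validation.

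How often this would mislead is conditional. It is small if the indicators are nearly uncorrelated and normal, about an even chance at correlation 0.2, and close to certain at 0.3 and above. These figures rest on assumed correlations and distributions, on all four variables being indicators, on a 0.05 test that the plan does not state, and on a Gaussian profile model standing in for an unspecified one. The change is worth making because it is cheap and Hypothesis 4 is a stated hypothesis of Aim 2.

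**What to change.** In the Hypothesis 4 text:
1. State that a variable used as a class indicator cannot serve as a validator.
2. Report class differences on the indicators as a description of the classes, without p-values.
3. Name validators in advance from measures in the section 5.0 screening list that are not indicators, for example AUDIT, the Short Inventory of Problems – Revised, the Impaired Control Scale, the Penn Alcohol Craving Scale and the Alcohol Purchase Task. Limit them to measures collected in all participants, because that section lets the investigator collect only part of the list.
4. Before claiming discrete subgroups, compare the class solution with a one-factor (dimensional) model on the same indicators. For four continuous indicators that model has 4 means + 4 loadings + 4 residual variances = 12 parameters, against 13 for two classes, so the two can be compared directly by BIC. If the factor model fits as well or better, report a graded trait.

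Cost: a few sentences and a little extra analysis, with no new procedure provided the chosen measures were collected in everyone. Downside: the replacement validators, AUDIT and the problem inventory above all, are only partly independent of AUD symptoms. This is why item 4 is needed alongside item 3.

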Our long-term goal is to use SDA as a platform for the laboratory testing of novel pharmacologic and behavioral interventions that can be used among those with the highest risk, but who have yet to progress to treatment-resistant drinking. The objective of this project is to test SDA across multiple levels of analysis. We consider SDA as an early marker of alcohol use disorder progression that is related to lifetime drinking history, alcohol use disorder risks, and brain physiology. Our current IARC pilot study (IRB #) demonstrates that SDA can be objectively quantified via an intravenous alcohol self-administration task, where operant work for identical incremental alcohol rewards is paired with aversive stimuli. Our preliminary data support our central hypothesis: that behavior in the SDA model is attributable to lifetime alcohol exposure, is related to alcohol use disorder (AUD) risk factors and phenotypes, and reflects alterations in neural system function. Specifically, they suggest that the degree of SDA is positively associated with recent drinking history, negative affect-based rash action (i.e. negative urgency, including action with respect to alcohol use), and self-rating of the effects of alcohol. The rationale for this work is that it would lead to the first objective, well-validated measure of SDA in humans.

Our specific aims are to:

*Aim 1:* Characterize SDA as a function of lifetime drinking history.

*Hypothesis 1:* Greater SDA will reflect greater lifetime drinking history.

*Hypothesis 2:* Those with a high lifetime drinking history will demonstrate less sensitivity to aversion in the preference to work for alcohol. Specifically, those with a high lifetime drinking history will work more for alcohol compared to water under both aversive and neutral experimental conditions, whereas those with a low lifetime drinking history will only work more for alcohol compared to water when alcohol seeking is paired with neutral stimuli.

Aim 2: Quantify associations between SDA and alcohol use disorder severity, and between SDA and risk phenotypes; then characterize how these risk factors classify individuals into those who will and will not work for alcohol in the context of aversive stimuli.

*Hypothesis 3:* Those with greater SDA will have greater AUD severity, greater negative urgency, a greater density of familial alcoholism, and reduced subjective, behavioral, and electrophysiologic sensitivity to alcohol.

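### Aim 2 and Hypothesis 4 speak of classifying individuals, but the only check against SDA is a between-class difference, which shows association and not correct classification

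*Combined protocol and SAP*

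**What the plan says.** Section 2.0 states the target in two ways. Aim 2 is to "characterize how these risk factors classify individuals into those who will and will not work for alcohol in the context of aversive stimuli". Hypothesis 4, listed under it, says that the Hypothesis 3 predictors that reach significance "will identify a latent trait that classifies individuals into two types: those who have high SDA and those who have low SDA".

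Section 7.0 (Aim 2 Hypothesis Testing Plan, Hypothesis 4) repeats the high/low form and then gives the method:

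- Class formation: "The significant phenotypes from hypothesis 3 will be used in a latent class analysis to identify subgroups based on" the pattern of AUD risk.
- Number of classes: BIC and entropy "will be utilized to determine the number of latent classes that best fit the data".
- Assignment: each person goes to the most probable class. The classes are then described on AUD criteria, negative urgency, family history density and lifetime drinking.
- Check against SDA: "As a final validator, we will test if SDA is different between the classes". The sentence goes on to give the purpose, which is to learn whether membership reflects motivation to work for alcohol under aversion.

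SDA itself is defined under Hypothesis 1 as a count of trials worked for alcohol in the aversive session. For Hypothesis 4 the plan gives no test statistic, alpha, high/low dividing line or measure of classification accuracy. It does not say what follows if the preferred number of classes is not two.

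**The concern.** A difference between groups and the correct sorting of individuals are separate claims. Two classes can differ clearly in SDA while their distributions overlap so much that membership says little about any one person.

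Nothing else in the plan fills the gap. Entropy measures how cleanly people separate on the risk indicators, not whether the classes agree with SDA. The other validators are candidate predictors from Hypothesis 3, and those found significant will also have formed the classes. The SDA comparison is therefore the only check against the stated target.

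It is also a favourable check. Phenotypes enter the class analysis because they were significant in a model whose dependent variable is aversive-session alcohol work, in the same participants.

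At stake is what Aim 2 and Hypothesis 4 may conclude. The analyses for Hypotheses 1–3, 5 and 6 are not affected.

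**Working it through.** **1. Targets side by side.**

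| Place | Target |
|---|---|
| Section 2.0, Aim 2 | will or will not work for alcohol under aversion |
| Sections 2.0 and 7.0, Hypothesis 4 | two classes, high and low SDA, no cut given |
| Section 7.0, final validator | SDA differs between a data-chosen number of classes |

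Only the third is tested.

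**2. The plan's own two-group figure.** Power Analyses gives 50 per group, effect size 0.64, power 0.90 and alpha 0.01, for high versus low lifetime drinking. No figure is given for latent classes. The noncentrality is 0.64 × √(50×50/100) = 3.2 on 98 df. Noncentral-t power is 0.716 at two-sided 0.01, 0.797 at one-sided 0.01 and 0.887 at two-sided 0.05. The stated 0.90 is therefore not reproduced at alpha 0.01 and is close only at two-sided 0.05. That is a separate matter, but for this reason both alphas are carried below.

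**3. Smallest significant difference.** Assume two classes of 50 and a t test; the plan names no statistic. Then d = t × √(1/50 + 1/50) = t × 0.2.

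- Two-sided 0.05: 1.984 × 0.2 = 0.397
- Two-sided 0.01: 2.627 × 0.2 = 0.525

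**4. Share on the wrong side.** Assume normal SDA with equal variance, equal classes and a midpoint cut (which is then also the overall median). The share is Φ(−d/2); guessing gives 50%.

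| d | Source | Wrong side |
|---|---|---|
| 0.397 | just significant, alpha 0.05 | 42.1% |
| 0.49 | smallest prior effect, Power Analyses | 40.3% |
| 0.525 | just significant, alpha 0.01 | 39.6% |
| 0.64 | plan's figure for lifetime-drinking groups | 37.4% |
| 1.31 | largest prior effect, Power Analyses | 25.6% |

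A 20% error share would need d = 2 × 0.842 = 1.68, above any prior self-administration effect that the plan quotes.

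**5. Sensitivity to class size and cut.** These are simulated with 30% or 20% in the high class and d from 0.40 to 0.64. A median cut gives about 40–45% wrong, and a cut matched to the class share gives about 26–36%. The error-minimising rule gives about 20–30%, but only by placing nearly everyone in the larger class. This is why accuracy has to be read against the base rate.

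**6. Direction of the AUC.** SDA predicting class has AUC Φ(d/√2), which is 0.61 at d = 0.397 and 0.67 at d = 0.64. Hypothesis 4 asks the reverse, class predicting SDA. With cleanly separated equal classes and a median split, that AUC is Φ(d/2), or 0.58 and 0.63.

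**7. Precision of an AUC at n = 100.** The Hanley–McNeil variance is [A(1−A) + (m−1)(u−A²) + (n−1)(v−A²)]/(mn), with u = A/(2−A) and v = 2A²/(1+A). At an assumed A = 0.70, u = 0.538 and v = 0.576.

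- 50/50 split: SE = √(6.82/2500) = 0.052, half-width about 0.10.
- 10/90 split: SE = √(5.30/900) = 0.077 or √(8.34/900) = 0.096, depending on which group is the smaller. The half-width is about 0.15 to 0.19.

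**The case against.** The best defence is that the SDA comparison does what it is meant to do. Forming classes from risk indicators and then comparing them on an external variable is a coherent way to ask whether membership reflects motivation, and the plan never promises an individual error rate. Aim 2 can be read as a one-line summary that Hypothesis 4 makes concrete as high versus low SDA. The structural equation model for Hypothesis 3 already relates the risk factors to SDA at the individual level.

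Much of this stands. The test is right for its stated purpose and should be kept. The defence does not rescue the classification claim: even if high/low SDA is accepted as the single target, it has no dividing line and no accuracy measure.

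Three stronger readings are tempting, and the documents do not support them:

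- *That not working means SDA of zero, an outcome the plan then fails to analyse.* No passage defines it so, and no share of non-workers is given.
- *That about 4 in 10 participants will be misclassified.* The figure depends on the assumptions above, and it falls to 26% at the plan's largest prior effect. The 0.64 belongs to lifetime-drinking groups, and applying it to latent classes is an assumption.
- *That a significant difference will be reported as proof of classification.* Hypothesis 4 has no stated decision rule. The plan permits that conclusion but does not commit to it.

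**Conclusion.** The point holds as a mismatch between claim and test. A between-class difference in SDA can show that class membership is associated with SDA. It cannot support the statement that risk factors classify individuals, whether as will/will not work or as high/low SDA.

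The size is an illustration of what a significant result would be compatible with: about 40–42% on the wrong side at the significance threshold, 37% at d = 0.64 and 26% at d = 1.31. It rests on equal classes, normal SDA, a midpoint cut and comparison by a t test. Other class shares and cuts move it in both directions.

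This is a cheap improvement to one hypothesis. It is not a flaw in the data collection or in the other aims.

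**What to change.** - Use one SDA target in Aim 2, in both statements of Hypothesis 4 and in the final-validator sentence.
- Report the two-class solution for Hypothesis 4, alongside any other number of classes that BIC and entropy prefer.
- Keep the SDA comparison, and word its conclusion as *SDA differs between classes*.
- Add a measure of how well the class posterior probability discriminates on SDA. This could be a concordance index on continuous SDA, or an AUC at one cut stated in advance. Give a 95% CI, and for the AUC also correct classification against the base rate.
- Correct that measure for optimism by cross-validation or bootstrap, repeating the selection of phenotypes within each resample.
- Do not state that risk factors classify individuals on the between-class test alone.

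The cost is a few wording changes and one analysis of data already being collected. The downside is that Hypothesis 4 becomes harder to support. The AUC will also be imprecise: about ±0.10 for a 50/50 split and about ±0.15 to 0.19 for a 10/90 split. This favours continuous SDA or a near-even cut.
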